**AUY922 intravenously at 70 mg/m^2 once weekly, i.e. days 1, 8 and 15 of every 21-day cycle**

Although it is ideal for patients to receive their study medication on the same day of the week each week, there is a 2-day plus/minus window allowed to be flexible with holidays, inclement weather, transportation difficulties, etc. For patients who are unable to tolerate the protocol-specified dosing schedule, schedule adjustments are permitted. This includes the ability to skip a week of dosing if needed up to once per cycle.

## **5.1 Pre-treatment Criteria**

### **5.1.1 Cycle 1, Day 1**

The patient should continue to meet all eligibility criteria on C1D1, as they did during the screening period.

### **5.1.2 Subsequent treatment days (weekly)**

- Any grade 3 or higher toxicity should have resolved to grade 1 or baseline prior to dosing
- ECG should be reviewed by a clinician to verify QTcF is not prolonged >500ms

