#### **6.2.2 Ocular Toxicity Management**

Weekly administration of AUY922 may cause visual symptoms. The visual symptom descriptions from ongoing phase studies have included slow dark-light adaptation or photophobia, blurred vision, floaters and flashes in peripheral vision, dark or black spots, darkening of vision, decreased peripheral vision, color vision disturbances, and dry eye syndrome. The visual symptoms were mostly reported the day after the second or third infusion and typically resolved within a week or two weeks post dose. All visual symptoms were reversible; in some patients the events resolved with omission of a dose or after discontinuation of AUY922 treatment.

The standard recommendation for managing visual toxicities with AUY is to hold the drug if toxicities are grade 2 or higher. See Section 6.3 for dose reduction guidelines.

Standard ophthalmologic assessments will be required at baseline and follow-up exams will be conducted at the time when visual symptom(s) are reported (if any), at the beginning of cycle 3 if no visual symptom(s) are reported, and at study discontinuation.

The following standard ophthalmologic assessments are required:

1. Visual acuity test
2. Intraocular pressure test
3. Slit-lamp test
4. Dilated fundus test
5. Color-vision (Ishihara-plate) test

Additional assessments or tests may be conducted as clinically indicated. Visual symptoms will be graded using NCI CTCAE 4.0. However, for the acuity test (Snellen charts) the following grading should be applied.

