**Table 5. Criteria for Interruption, Dose Reduction and Re-Initiation of AUY922**

| Recommended Dose Modifications for AUY922                                |   |
|--|---|
| Worst Toxicity
CTCAE Grade a unless otherwise
specified | At any time during a cycle of AUY922
(including intended day of dosing)  |
| No toxicity   | Maintain dose level  |
| Diarrhea  |   |
| Grade 1 (see Section 6.2 for recommended treatment algorithm)            | Maintain dose level   |
| Grade 2
(see Section 6.2 for recommended treatment algorithm)         | Omit dose administration until recovery to Grade 1 or baseline, then continue AUY922 at:
- current dose level if grade 2 toxicity persisted ≤ 7 days.
- one dose level lower if grade 2 toxicity persisted > 7 days   |
| Grade 3
(see Section 6.2 for recommended treatment algorithm)         | Omit dose administration until recovery to Grade 1 or baseline then decrease the next scheduled dose by 1 dose level.   |
| Grade 4
(see Section 6.2 for recommended treatment algorithm)         | Omit dose administration until recovery to Grade 1 or baseline then:
- if grade 4 toxicity lasted ≤ 24 hours, may resume AUY922 but decrease the next scheduled dose by 1 dose level.
- In the event Grade 4 toxicity lasted >24 hours despite maximal medical attention, permanently discontinue treatment.

If grade 4 toxicity recurs upon re-exposure, permanently discontinue treatment. |

| Recommended Dose Modifications for AUY922  |   |
|---|---|
| Worst Toxicity
CTCAE Grade a unless otherwise
specified                                       | At any time during a cycle of AUY922
(including intended day of dosing)  |
| Hematological  |   |
| Neutropenia (ANC)
Grade 1 (ANC < LLN - $1.5 \times 10^9/L$ ) or
Grade 2 (ANC < $1.5 - 1.0 \times 10^9/L$ ) | Maintain dose level   |
| Grade 3 (ANC < $1.0 - 0.5 \times 10^9/L$ )  | Omit dose administration until resolved to $\leq$ grade 1,

 
• If resolved in <math>\leq</math> 7 days, then maintain dose level
 
• If resolved in <math>></math> 7 days, then decrease by 1 dose level
 
       |
| Grade 4 (ANC < $0.5 \times 10^9/L$ )  | Omit dose administration until resolved to $\leq$ grade 1, then
decrease by 1 dose level   |
| Febrile neutropenia   | Omit dose administration until resolved, then decrease by 1
dose level   |

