| Grade 3 (>5.0 - 20.0 x ULN )  | Omit dose administration until resolved to ≤ grade 1 (or ≤ grade 2 in case of liver metastasis), then 

• If resolved in ≤ 7 days, then maintain dose level

• If resolved in > 7 days, then decrease by 1 dose level

   |
| Grade 4 (> 20.0 x ULN)  | Omit dose administration until resolved to ≤ grade 1, then decrease by 1 dose level   |
| Cardiac - Prolonged QTcF interval  |   |
| During cycle 1  |   |
| Absolute QTcF ≤ 480msec   | Maintain dose level and ECG monitoring as per visit schedule.   |
| Absolute QTcF ≥ 481msec and, ≤ 500 msec   | Maintain dose level. ECG monitoring assessments should be performed for 2 additional cycles at the same frequency as in cycle 1. After the second additional cycle, ECGs for subsequent cycles will be performed as follows: 

• If ECG in the additional cycles shows no QTcF absolute ≥ 481 msec then, for subsequent cycles ECG monitoring will be performed as per visit schedule.

• If ECG still abnormal (QTcF absolute ≥ 481 msec and ≤ 500 msec) then ECG monitoring must continue at the same frequency as in cycle 1 for all subsequent cycles.

 |

| Recommended Dose Modifications for AUY922  |  |
|---|--|
| Worst Toxicity
CTCAE Grade a. unless otherwise
specified                | At any time during a cycle of AUY922
(including intended day of dosing)   |

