| During any cycle
Grade 3 or QTcF $\geq$ 501 msec as identified by the investigator on the ECG. | 
Omit dose administration. Monitor patient with hourly ECGs until the QTcF has returned to <math>\leq</math> 450 msec. Further monitoring as clinically indicated. Exclude other causes of QTcF prolongation such as hypokalemia, hypomagnesemia and blood oxygenation statusb.
 
Once QTcF prolongation has resolved, patients may be re-treated at one lower dose level at the investigator's discretion. ECG monitoring must continue throughout the treatment period as follows:
 

• ECG monitoring assessments should be performed for 2 additional cycles at the same frequency as in cycle 1

• If the ECGs obtained in the first and second additional cycle (after dose reduction) are without any QTcF prolongation, then ECG monitoring in subsequent cycles will be continued as per the visit schedule.

• If the patient had an absolute QTcF <math>\geq</math> 481 msec and <math>\leq</math> 500 msec, then ECG monitoring at the same frequency as in cycle 1 will be continued for all subsequent cycles.

• Patients who experience absolute QTcF <math>\geq</math> 501 msec after one dose reduction will be discontinued from study.

 
Note: If Torsades de Pointes are observed in a patient, the patient will be discontinued from the study.
 |

| Recommended Dose Modifications for AUY922  |   |
|---|---|
| Worst Toxicity
CTCAE Grade a unless otherwise
specified   | At any time during a cycle of AUY922
(including intended day of dosing)  |
| Other adverse events   |   |
| Grade 1 or 2  | Maintain dose level   |
| Grade 3   | Omit dose administration until resolved to ≤ grade 1, then decrease by 1 dose level   |
| Grade 4   | Omit dose administration and permanently discontinue patient from study   |
| Eye disorders (see section 6.2 for Grading Table)  |   |
| Grade 1   | Maintain dose level   |
| Grade 2   | Omit dose administration until resolved to ≤ grade 1 (or baseline), then continue treatment with AUY922 at the current dose level
If visual symptoms ≥ Grade 2 recur upon re-exposure to AUY922, omit dose until resolution to ≤ Grade 1, then decrease 1 dose level |
| Grade 3   | Omit dose administration until resolved to ≤ grade 1 (or baseline), then decrease 1 dose level  |

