| Grade 4   | Omit dose administration and permanently discontinue patient from study   |
| All dose modifications should be based on the worst preceding toxicity.   |   |
| If a patient requires a treatment interruption of > 21 days from the last dose of AUY922, then the patient must be discontinued from the study treatment. Patients who discontinue from the study for a study-related adverse event or an abnormal laboratory value must be followed as per protocol.   |   |
| - Up to two dose reductions are allowed. In case the patient had clinical benefit and needs more than two dose reduction, it will be discussed case by case with the sponsor  |   |
| a Common Terminology Criteria for Adverse Events (CTCAE Version 4.0)   |   |
| b Exclude other causes of QTc prolongation such has hypokalemia, hypomagnesemia and blood oxygenation status. Patients who develop hypokalemia or hypomagnesemia during the study should receive electrolyte replacement as soon as possible and should not receive further AUY922 dosing until the respective electrolytes are documented to be within normal limits. |   |

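### The weekly pre-dose criteria in 5.1.2 and the hold and restart rules in Section 6 cover the same dosing day but are not aligned; for grade 3 AST/ALT with liver metastases they contradict each other

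*Combined protocol and SAP*

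**What the plan says.** All references are to the combined protocol and SAP.

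- **Section 5.1.2 (pre-treatment criteria, weekly dosing days)** has two lines: "Any grade 3 or higher toxicity should have resolved to grade 1 or baseline prior to dosing" and "ECG should be reviewed by a clinician to verify QTcF is not prolonged >500ms". It contains no reference to Section 6.
- **Section 6.2.2 (ocular toxicity):** "The standard recommendation for managing visual toxicities with AUY is to hold the drug if toxicities are grade 2 or higher".
- **Section 6.3 (general rule):** after unacceptable toxicity, drug is suspended until return to grade 1 or lower, or to baseline.
- **Table 5** applies throughout a cycle, "including intended day of dosing". For grade 3 AST/ALT it says "Omit dose administration until resolved to ≤ grade 1 (or ≤ grade 2 in case of liver metastasis". It also withholds the dose for grade 2 diarrhea, grade 2 eye disorders, grade 2 thrombocytopenia, and creatinine or bilirubin at 2-3 x ULN. For QTcF of 501 msec or more it withholds the dose and says "Monitor patient with hourly ECGs until the QTcF has returned to" 450 msec or less; re-treatment follows once the prolongation has resolved.
- **Table 5, footnote b:** patients who develop hypokalemia or hypomagnesemia during the study "should not receive further AUY922 dosing until the respective electrolytes are documented to be within normal limits". The footnote marker is on the QTcF row for 501 msec or more.

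**The concern.** Section 5.1.2 is where staff would look on a treatment day. If its criteria differ from Table 5, two clinicians following the protocol can reach opposite decisions on the same patient. The documents name three participating clinics and up to three doses per 21-day cycle, so the decision recurs often. Dosing-day safety is at stake first. Safety and tolerability is also a secondary objective (Section 1.3), and holds applied by different rules would make that summary harder to interpret.

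**Working it through.** No plan figure bears on this point and no arithmetic applies. The check sets the rules side by side for one patient on one dosing day.

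**1. AST/ALT with liver metastases**

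Inputs: Section 3.1.7 admits AST/ALT up to 3.0 x ULN, or up to 5.0 x ULN with liver metastases. Table 5 places grade 1 at up to 3.0, grade 2 at above 3.0 to 5.0 (ALT, asymptomatic) and grade 3 at above 5.0 to 20.0 x ULN. Take a patient whose value reached grade 3 and has fallen to grade 2 on the dosing day, reading baseline as the baseline grade.

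| Patient | Table 5, grade 3 row | 5.1.2 | 6.3 general rule |
|---|---|---|---|
| No liver metastases | Hold | Hold | Hold |
| Liver metastases, baseline grade 2 | Restart allowed | Met through baseline | Met through baseline |
| Liver metastases, baseline below grade 2 | Restart allowed | Not met | Not met |

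Only the third row is in conflict, but there the passages are irreconcilable as written. Section 5.1.2 is the stricter rule in that row, so treating it as a minimum to which Table 5 adds further holds does not explain the difference.

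**2. Holds below grade 3**

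| Finding on the dosing day | 5.1.2 | Section 6 |
|---|---|---|
| Grade 2 eye disorder | Silent | Hold (6.2.2, Table 5) |
| Grade 2 diarrhea | Silent | Hold (Table 5) |
| Grade 2 thrombocytopenia | Silent | Hold (Table 5) |
| Creatinine or bilirubin 2-3 x ULN | Silent | Hold (Table 5) |

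Section 5.1.2 is silent here rather than permissive. A site that applies Section 6 complies with every passage; a site that uses 5.1.2 alone as its checklist misses all four rows.

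**3. Electrolytes, within Table 5**

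The text of footnote b covers any patient who develops low potassium or magnesium during the study, with no grade threshold. Its marker ties it to one QTcF row. Under Section 10.1.1 a laboratory abnormality that needs treatment is an adverse event, so a grade 1 or 2 case that is being replaced also falls in the Other adverse events row, which keeps the dose level unchanged and mentions no hold. Elsewhere Table 5 spells out a hold followed by the same dose level where it intends one (for example, grade 3 neutropenia resolved within 7 days). Whether footnote b applies outside the QTcF row is therefore unclear.

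**4. QTcF**

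The triggers agree: above 500 ms in 5.1.2, and 501 msec or more in Table 5. The restart conditions are worded differently. Table 5 uses 450 msec for ending hourly ECGs and resolution for re-treatment. Section 5.1.2 uses grade 1 or baseline together with not above 500 ms. Section 3.2.11 excludes a screening QTcF of 450 ms or more, so the baseline condition lies close to Table 5's value. Whether the grade 1 condition differs in substance depends on a CTCAE band that the documents do not reproduce.

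**The case against.** The strongest defence is that 5.1.2 lists necessary conditions and nowhere says they are sufficient. The opening of Section 5 sends dose modifications to Section 6, Section 6 says it is the basis for delays and modifications, and Table 5 expressly covers the dosing day. For the grade 2 holds this defence stands. A reader might infer that 5.1.2 clears a patient with grade 2 visual toxicity or diarrhea, but it does not say so; what remains is a missing pointer.

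Two other inferences also go too far. One is that 5.1.2 clears any QTcF up to 500 ms after a prolongation. That reads its ECG line alone: Table 5 treats the event as grade 3, so the toxicity line of 5.1.2 applies too. The other is that footnote b contradicts 5.1.2. The tension is inside Table 5, and waiting for normal values and then resuming at the same level would satisfy both its row and its footnote.

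For AST/ALT, it can be said that the specific Table 5 row is an exception to the general rules and that the affected group is narrow. The narrowness is conceded. The precedence is plausible but unstated: neither 5.1.2 nor 6.3 mentions an exception, and Table 5 is titled as recommended modifications.

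**Conclusion.** The point holds in a limited form: one direct contradiction (grade 3 AST/ALT with liver metastases and baseline below grade 2), one missing cross-reference, one footnote of unclear scope, and one pair of QTcF restart conditions that should be aligned.

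The size cannot be given as a number. The documents report no frequency for the AST/ALT case. A reader might take the 77% visual and 74% diarrhea rates from the earlier phase 2 study (Section 2.1.3) as the measure. They are all-grade rates, and they concern toxicities for which the passages can be read together, so they do not measure the contradiction. Divergent practice between clinics is a risk, not something the documents show, and Section 13 plans no dose-intensity analysis that would be distorted. The primary endpoint rule and the Simon two-stage figures are unaffected.

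The conclusion assumes that baseline in 5.1.2 and 6.3 means the patient's baseline grade, and that no precedence rule lies in text removed from the public document.

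**What to change.** The sponsor should reconcile 5.1.2, 6.2.2, 6.3, Table 5 and footnote b, and state which passage governs dosing-day decisions. The amendment should:

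- settle the AST/ALT restart condition with liver metastases, so that 5.1.2, 6.3 and Table 5 give one answer;
- add a cross-reference in 5.1.2 to the Section 6 holds;
- state the scope of footnote b relative to the Other adverse events row;
- use one wording for the QTcF restart condition.

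Which clinical rule is right is for the sponsor to decide; nothing here implies that Table 5, or 5.1.2, should prevail. The cost is amendment wording and an updated dosing-day checklist, with no change to sample size, endpoints or analysis.

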## **5.2 AUY922 Administration**

### **5.2.1 How AUY922 is supplied**

Novartis supplies AUY922 in individual vials and/or amber-colored, glass ampoules. Vials will also be available. Each vial is 20mL, each containing nominally 50 mg AUY922 (calculated as free base). The storage conditions for study drug will be described on the medication label. The vials/ampoules should be stored safely and separately from other drugs. Please see handling instructions.

#### **Dosage Forms:**

**Vials:** 20 mL vials, each containing nominally 50 mg AUY922 (calculated as free base).

**Glass ampoules:** 10 mL amber-colored, glass ampoules, each containing 10 ml of a 5 mg/ml active drug substance in 5% aqueous glucose solution.

### **5.2.2 Preparation and storage for AUY922**

AUY922 is intended for IV infusion and should be diluted to the appropriate concentration (according to patient body surface area) in a 500ml infusion bag containing 5% dextrose or glucose (with a maximum infusion volume of 500 ml) prior to administration. Note that concentrations within the range of 0.006 mg/ml up to 0.28 mg/ml are acceptable. The drug may be administered using a central line or via peripheral vein. If a peripheral line is used, the injection site should be monitored carefully during the time of infusion and at subsequent follow-up visits.

Please follow the preparation instruction provided below.

The image is a high-contrast, black-and-white abstract graphic. It features a grid of horizontal bars of varying lengths, primarily black, set against a white background. The bars are arranged in a roughly rectangular frame. On the far left, there is a vertical column of white squares of varying sizes, creating a stepped, staircase-like effect. The overall composition is minimalist and geometric, with a focus on form and space.

**Storage Information:**

### 5.3 Administration of AUY922

- AUY922 will be administered to patients through a 0.2 µm in-line filter.

14. Once the AUY922 Concentrate for Infusion has been compounded in the infusion bag, it should be administered immediately.

15. The infusion set has to be flushed with a carrier solution (5% dextrose) prior administration of the infusion solution.

16. From a microbiological point of view, the aseptic techniques, in-use storage time (60 minutes) and conditions prior to use are the responsibility of the person who is administering the infusion (e.g. hospital pharmacist / nurse).

17. From a chemical - and physicochemical point of view, in-use stability of AUY922 infusion solution has been demonstrated for a maximum of 6 hours at room temperature and at 2-8°C (opening of the Vials until end of infusion).

18. Carefully inspect the final infusion solution prior to administration. The final infusion solution should be a clear solution free from any particles.

19. The final infusion solution must be administered through an integrated or additional 0.2 µm in-line filter.

### 5.4 Definition of Dose-Limiting Toxicity

N/A

### 5.5 General Concomitant Medication and Supportive Care Guidelines

In general, the use of any concomitant medication/therapies deemed necessary for the care of the patient is permitted with the following exceptions:

- Therapeutic doses of warfarin sodium (Coumadin®) are not permitted.
- Preliminary *in vitro* metabolism studies suggest that AUY922 is a moderate CYP2C9, 2C8, 2C19, and CYP3A4 inhibitor. Therefore, drugs known to be metabolized by CYP3A4, CYP2C8, CYP2C9 or CYP2C19 should be used with caution because of the inherent potential risk of either reduced activity or enhanced toxicity of the respective concomitant medication and/or AUY922 with preliminary *in vitro* metabolism studies. Patients using concomitant medications known to be metabolized by these cytochrome p450 isoenzymes will not be excluded from the study. However, the patients must be carefully monitored for potentiation of toxicity due to individual concomitant medications.
- Please refer to a list of known medications that are substrates, inhibitors, and inducers of CYP2C9, CYP2C8, 2C19, and 3A4/5 enzymes and avoid co-administration with AUY922 in *For the most updated information, please also visit the following website: [medicine.iupui.edu/flockhart/table.htm](http://medicine.iupui.edu/flockhart/table.htm)*

If, after a patient has been enrolled, he/she requires the concomitant use of any of the medications which may cause QT prolongation, then the patient must be discontinued from the study. Excluded medications which may cause QTc prolongation are also listed and updated in web address: [qtdrugs.org/medical-pros/drug-lists/drug-lists.htm](http://qtdrugs.org/medical-pros/drug-lists/drug-lists.htm). The investigator should instruct the patient to notify the study site about any new medications he or she takes after the start of the study drug.

## 5.6 Duration of Therapy

Duration of therapy will depend on individual response, evidence of disease progression and tolerance. In the absence of treatment delays due to adverse events, treatment may continue until one of the following criteria applies:

- Disease progression.
- Intercurrent illness that prevents further administration of treatment,
- Unacceptable adverse event(s),
- Participant decides to withdraw from the study, or
- General or specific changes in the participant's condition render the participant unacceptable for further treatment in the opinion of the treating investigator.

Patients may continue to receive AUY922 beyond RECIST-defined progression at the discretion of the treating physician if they are continuing to show clinical benefit.

## 5.7 Duration of Follow Up

Participants will be followed for survival every 3 months after removal from study or until death, whichever occurs first. Participants removed from study for unacceptable adverse events will be followed until resolution or stabilization of the adverse event.

## 5.8 Criteria for Removal from Study

Participants will be removed from study when any of the criteria listed in Section 5.5 applies. The reason for study removal and the date the participant was removed must be documented in the study-specific case report form (CRF). Alternative care options will be discussed with the participant.

In the event of unusual or life-threatening complications, participating investigators must immediately notify the Principal Investigator (or Protocol Chair), [name], at [REDACTED]

